17.4. Secondary Objective

The secondary objective, Quality of Life, will be evaluated to gain additional information about the performance of the Arctic Front Advance Cardiac CryoAblation catheter.

There are three hypotheses tested in the objective, hypothesis tests for AFEQT questionnaire, the physical component score of the SF-12 questionnaire, and the mental component score of the SF-12 questionnaire. A Hommel multiple testing procedure will be utilized to maintain an overall type I error rate of 0.025 for this objective²².

The Hommel procedure is a stepwise procedure and will be implemented following the below.

The three hypothesis will be defined as H(1), H(2), and H(3). For each of the hypotheses, p-values will be calculated and sorted $p(1) < p(2) < p(3)$. The decision rule to accept or reject each hypothesis will follow the step-up algorithm, where $\alpha=0.025$:

Step 1: If $p(3) > \alpha$, accept H(3) and go to Step 2, otherwise reject all hypotheses and stop

Step 2: If $p(2) > \alpha/2$, accept H(2) and go to Step 3, otherwise reject all remaining hypotheses and stop

Step 3: If (1) $\alpha/2 < p(2) \leq 2\alpha/3$ and $p(1) \leq \alpha/2$ or (2) $p(1) \leq \alpha/3$, reject H(1); otherwise accept H(1)

17.4.1. Secondary Objective: Quality of Life - Atrial Fibrillation Effect on Quality-of-life (AFEQT) and SF-12 Questionnaires

Demonstrate an improvement in quality of life between baseline and 12 months as measured by the AFEQT and SF-12 questionnaires.

²² Hommel, G. A stagewise rejective multiple test procedure based on a modified Bonferroni test. *Biometrika* 1988; 75, 383-386.

17.4.1.1. Atrial Fibrillation Effect on Quality-of-life (AFEQT)

Hypothesis

The following hypothesis will be tested in a one-sided test at the 0.025 significance level:

Ho: $\Delta\text{AFEQT} = 0$

Ha: $\Delta\text{AFEQT} > 0$

Where ΔAFEQT is the change in AFEQT score from baseline to 12 months.

Endpoint Definition

The AFEQT questionnaire will be utilized for this objective. The questionnaire is an atrial fibrillation specific health-related quality of life questionnaire to assess the impact of AF on a subject's life. The overall score ranges from 0 – 100, with 0 corresponds to complete disability and 100 corresponds to no disability.

Analysis Methods

Change in AFEQT score is defined as 12-month AFEQT score minus baseline AFEQT score. Change in AFEQT scores will be assessed utilizing a one-sample t-test. A two-sided 95% confidence interval will be calculated based on the t-distribution.

Additionally, summary statistics (e.g. mean, SD, median, range) and graphical methods will be used to summarize the change in AFEQT scores from baseline through 12 months.

Performance criteria

If the p-value from the one-sample t-test after adjusting for the Hommel procedure is < 0.025 , the objective will be considered met.

Determination of Subjects/Data for Analysis

All enrolled subjects who have the Arctic Front Advance Cardiac CryoAblation Catheter inserted into vasculature and have completed baseline and 12 month questionnaires will be included.

Additional Analyses

The AFEQT questionnaire has three subscale scores, Daily Activities Subscale, Treatment Concern, and Treatment satisfaction. Each subscale ranges from 0 – 100, where 0 corresponds to low quality-of-life and 100 corresponds to high quality of life.

Change in AFEQT subscale score is defined as 12-month AFEQT subscale score minus baseline AFEQT subscale score. A two-sided 95% confidence interval will be calculated based on the t-distribution.

Medtronic Confidential

[Redacted text block containing multiple paragraphs of blacked-out content]

Medtronic Confidential

STOP Persistent AF Clinical Investigation Plan

Version 6, 01DEC2017

Page 77 of 128

[Redacted text block]

Medtronic Confidential

[Redacted text block containing multiple lines of blacked-out content]

18. Ethics

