13.10.3. Six Month Office Visit

- Review medications
- Adverse event assessment
- Review symptoms suggestive of recurrent AF/AT/AFL
- 12-lead ECG
 - Send to the core lab
- 24h continuous monitoring with Holter
 - Send to the core lab
- SF-12 Health Survey and AFEQT Questionnaire

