As with AFEQT assessments, SF-12 scores will be assessed as 6-month visits in addition to baseline and 12-month visits. While only the baseline and 12-month assessment will be used in the hypothesis tests for one-year change in SF-12 physical and mental health scores, all graphical and descriptive presentations of SF-12 outcomes will show data from all three timepoints. Additionally, results from a repeated measures analysis using all available data may be shown in the final report, to provide information on the degree of change in QoL in the first and second half years after the cryoablation procedure. The following code for SAS proc mixed provides a template for this analysis:

```
proc mixed data=...;
  class ...;
  model ...;
  ods output ...;
run;
```

```
proc mixed data=...;
  class ...;
  model ...;
  ods output ...;
run;
```

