6.8. Changes to Planned Analysis

Comprehensive details on analysis methods have been included to this SAP, but no changes to the statistical methods or principal features defined in the STOP AF First CIP version 5 are noted. However, there are two minor additions from the methods defined in the STOP Persistent AF CIP version 5. First, clarification has been added that while this study assesses subjects' QoL at six month follow-ups, and results from 6-month assessments will be made available in graphs and tables, the endpoints for the secondary objective are defined based only on QoL at baseline and 12 months. An additional repeated measures analysis may be performed outside of the analysis pre-specified for the secondary objective that utilizes data from all three points of assessment. Second, [REDACTED] was added to ancillary objective [REDACTED]

Additional analysis or deviations from procedures in this SAP may be addressed by the release of newer SAP versions, or will be described in the final report and/or main manuscript, along with the rationale for the deviation.

7. Determination of Sample Size

Sample size for STOP Persistent AF was determined by finding the minimum number of subjects enrolled which provides adequate power to both the hypothesis test for the primary efficacy objective, as well as the hypothesis test for the primary safety objective. Calculations are provided separately for each primary endpoint.

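### The quality-of-life tests use only subjects with a 12-month form and leave out the 6-month scores, so their 2.5% level is not protected if poor responders leave

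*Protocol*

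**What the plan says.** - **Error rate.** CIP 17.4 covers three hypotheses (AFEQT, SF-12 physical, SF-12 mental): "A Hommel multiple testing procedure will be utilized to maintain an overall type I error rate of 0.025 for this objective".
- **Test.** CIP 17.4.1.1: "The following hypothesis will be tested in a one-sided test at the 0.025 significance level", and "Change in AFEQT scores will be assessed utilizing a one-sample t-test". The null is zero mean change from baseline to 12 months.
- **Subjects.** CIP 17.4.1.1 limits the analysis to subjects with the catheter "inserted into vasculature and have completed baseline and 12 month questionnaires will be included". SAP 6.2.4.1 accepts AFEQT forms with at least half the items of each subscale at both visits. The SAP's SF-12 text uses complete cases in the mITT set.
- **6-month data.** The 6-month visit (CIP 13.10.3) includes "SF-12 Health Survey and AFEQT Questionnaire". In the SF-12 additional analyses under SAP 6.2.4: "While only the baseline and 12-month assessment will be used in the hypothesis tests". SAP 6.8 says the same of the secondary objective as a whole and adds: "An additional repeated measures analysis may be performed outside of the analysis pre-specified for the secondary objective".
- **Missing data.** SAP 6.2.4.3 re-runs the tests with missing baseline answers at the best level and missing follow-up answers at the worst. If significance changes, this is noted, and milder assumptions may be explored. The success criterion stays as it was.
- **Gate.** SAP 6.5 tests quality of life only if the primary objectives are met.

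**The concern.** This is a before-after comparison against zero in one arm. If subjects who did not improve are missing at 12 months, the mean change among the rest moves directly towards success, and no control arm moves with it. The Hommel procedure takes its p-values as given, so it controls error only if each p-value is valid. That requires the missing 12-month scores to be unrelated to the change in quality of life.

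The plan collects a 6-month score that could explain part of the missingness, and CIP 13.19 says data up to exit will be used. The deciding test nevertheless discards a leaver's baseline and 6-month scores. What is at stake is the claim of improved quality of life and the size of the reported gain. The SF-12 components would be the most exposed if their true change is small.

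**Working it through.** **1. The plan's own level.** Simulating three one-sample t-tests with the Hommel steps as written (N = 150, 40,000 runs) gives family error 0.0254, 0.0231 and 0.0186 with no dropout, for correlation between endpoints of 0, 0.5 and 0.8. With 10% random dropout it is 0.0243, 0.0235 and 0.0193. The stated 0.025 is therefore reproduced when missingness is unrelated to outcome.

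**2. Inputs.** From the documents: 150 treated and 10% attrition, so 150 × 0.9 = 135 with 12-month data; one-sided 0.025; null of zero. Assumed, because the documents give none: normal scores with unit SD and correlations of 0.5 (baseline to 6 months), 0.5 (baseline to 12 months) and 0.7 (6 to 12 months).

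**3. Bias by hand.** The variance of each change is 1 + 1 − 2(0.5) = 1. The covariance of the 6-month and 12-month changes is 0.7 − 0.5 − 0.5 + 1 = 0.7. If leavers' 6-month change is δ SD worse than completers', their expected 12-month change is 0.7δ worse. With a true overall mean of zero and 10% leaving, the completers' mean change is 0.10 × 0.7δ = 0.07δ. The test's error is then about 1 − Φ(1.96 − 0.07δ√135), with √135 = 11.62:

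- δ = 0.5: shift 0.035 × 11.62 = 0.407; 1 − Φ(1.553) = 0.060
- δ = 1.0: shift 0.070 × 11.62 = 0.813; 1 − Φ(1.147) = 0.126
- δ = 1.5: shift 0.105 × 11.62 = 1.220; 1 − Φ(0.740) = 0.230

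**4. Simulation.** The comparison is the completer t-test against the 12-month-minus-baseline contrast from an unstructured-covariance maximum-likelihood model (4,000 runs, Monte Carlo SE about 0.0025). Dropout is 10%, logistic with log-odds slope 1 or 2 per SD of poor change, or, as an extreme, the worst 10% all leave. Entries are one-sided error for slope 1 / slope 2 / worst 10%.

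| Leaving depends on | Completer t-test | Repeated-measures contrast |
|---|---|---|
| 6-month change, score recorded | 0.115 / 0.228 / 0.405 | 0.025 / 0.024 / 0.027 |
| same, half leave before the 6-month form | 0.115 / 0.228 / 0.405 | 0.046 / 0.060 / 0.087 |
| same, all leave before it | 0.115 / 0.228 / 0.405 | 0.070 / 0.121 / 0.229 |
| unseen 12-month change, 6-month score recorded | 0.192 / 0.432 / 0.724 | 0.081 / 0.156 / 0.337 |

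In the last row, if the 6-month score is missing too, the contrast's error at slope 2 is about 0.29. If dropout is unrelated to quality of life, both methods hold about 2.5%.

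**5. Sensitivity.** With the 6-to-12-month correlation between 0.5 and 0.85, the completer error in the first row is 0.085–0.146 (slope 1) and 0.168–0.317 (slope 2). At base correlations it is 0.059 and 0.090 with 5% dropout, and 0.267 and 0.563 with 20%. For the whole Hommel family at 10% dropout, with leaving driven by a score correlated 0.6 with the 12-month AFEQT change, error is 0.055–0.070 (slope 1) and 0.101–0.131 (slope 2).

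**6. The planned worst case.** Assume an AFEQT baseline mean of 50, SD 20 for baseline and for change, and 10% of 12-month scores set to 0.

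- True gain 0: mean change −0.1 × 50 = −5; variance 400 + 0.09 × 50² = 625; SE 25/√150 = 2.04; t about −2.5.
- True gain 10: mean change 0.9 × 10 − 5 = 4; variance 400 + 0.09 × 60² = 724; SE 26.9/√150 = 2.20; t about 1.8, not significant.

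The plan thus has a test that can be optimistic and a bound that can reject a real gain, with nothing pre-specified between them.

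**The case against.** The strongest reply is that the plan already deals with missing scores. A positive result that survives SAP 6.2.4.3 holds under any dropout mechanism, which a missing-at-random model cannot promise. That is right and is a reason to keep the analysis. But success does not depend on it, and step 6 shows that failing it says little.

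Second, the dropout premise has no support in the documents. Lack of efficacy is not a listed exit reason (CIP 13.19), and follow-up after a permitted repeat ablation in the blanking period stays on the index schedule (CIP 13.8). If subjects doing well skipped the last visit, the test would be conservative. This stands: the inflation is conditional. A reader might infer that the plan's true error rate is 6% to 23%. The documents do not support that.

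Third, the bias is modest. Significance with 135 subjects needs an observed mean change of about 1.98/√135 = 0.17 SD, and steps 3's biases for δ up to 1.0 are at most 0.07 SD. A large true gain would make the zero null academic, although the estimate would remain biased. Quality of life is also secondary and gated.

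Two further inferences go too far. The 6-month scores are not excluded altogether: they appear in tables and graphs and may enter the optional model. Nor would a repeated-measures test largely repair the problem whatever the mechanism. The last three rows of the table show otherwise, and the early-exit visit (CIP 13.11) lists no questionnaire, so subjects who leave early may have only a baseline score.

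Finally, parts of the SF-12 text and the model code are not visible, so the existing template cannot be taken to give the needed contrast.

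**Conclusion.** The point holds in conditional form. The deciding tests are restricted to completers, ignore a 6-month score that is collected, and hold 2.5% only if missingness is unrelated to quality of life. Under dropout driven by poor 6-month change, at 10% attrition and the assumed correlations, single-test error is about 6% (leavers 0.5 SD worse) to 23% (slope 2).

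The repeated-measures contrast returns error to about 2.5% when recorded baseline and 6-month scores explain leaving. Over the same range of selection it leaves about 3–6% if half leave before 6 months, 4–12% if all do, and 5–29% if leaving follows the unseen 12-month change. It was less biased than the completer test in every selective-dropout scenario examined and no worse under random dropout. All these figures rest on assumed correlations and mechanisms. The change is worth making, but it concerns a secondary objective and does not touch study success on the primaries.

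**What to change.** In CIP 17.4.1 and SAP 6.2.4.1–6.2.4.2, before data are analysed:

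1. Make the hypothesis test the 12-month-minus-baseline contrast from a repeated-measures model with visit (baseline, 6, 12 months) as a category, unstructured covariance, and all mITT subjects with at least one score. Feed its one-sided p-value into Hommel. With complete data its estimate equals the planned mean change.
2. Keep the completer t-test as supportive and retain the SAP 6.2.4.3 worst case.
3. Add a graded delta or tipping-point analysis of missing 12-month scores, to cover departures before 6 months and unseen later decline.

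Cost: no new data are needed, but the model must be written out in the SAP. The test then relies on missing-at-random given the recorded scores, a weaker assumption than the completer test makes. It also changes a method named in the CIP. CIP 17.1 requires an amendment only if a principal feature changes; otherwise the change and its justification go in the study report.

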18.1. Statement(s) of Compliance

The study will be conducted in compliance with international ethical and scientific quality standards, known as good clinical practice (GCP). GCP includes review and approval by an independent Ethics Board/Institutional Review Board (IRB)/Medical Ethics Committee (MEC)/Head of Medical Institution (HOMI) before initiating a study, continuing review of an ongoing study by an Ethics Board, and obtaining and documenting the freely given informed consent of a subject before initiating the study.

The study was designed to reflect the GCP principles outlined in ISO 14155:2011 and other international clinical requirements outlined below. These include the protection of the rights, safety and well-being of human subjects, controls to ensure the scientific conduct and credibility of the clinical investigation and the

Medtronic Confidential

definition of responsibilities of the sponsor and Investigators. In accordance with ISO standard, the sponsor shall avoid improper influence on, or inducement of, the subject, monitor, any Investigator(s) or other parties participating in or contributing to the clinical investigation. All Investigators shall avoid improper influence on or inducement of the subject, sponsor, monitor, other Investigator(s) or other parties participating in or contributing to the clinical investigation. The ISO standard also informed study design in the areas of device deficiency reporting and risk evaluation, with the exception (to the ISO standard) that only those Adverse Events (AEs) which are cardiovascular, serious, system (cryoablation and [REDACTED]) related and procedure related will be collected. This ensures any AEs which could potentially be relevant will be collected. There is a second exception (to the ISO standard) that device accountability will not be performed in Europe or Canada and only upon package opening in the US (full device accountability will take place in Japan starting with distribution).

The study will be conducted according to federal, national and local laws, regulations, standards, and requirements of the countries/geographies where the study is being conducted. In Europe, the study will also be conducted in accordance with the Declaration of Helsinki 2013. For all geographies, the principles of the Declaration of Helsinki have been implemented through the patient informed consent (IC) process, Ethics Board/IRB/MEC approval, study training, clinical trial registration, preclinical testing, risk-benefit assessment and publication policy.

Ultimately, all centers in all geographies will follow and comply with:

- Principles of Declaration of Helsinki (including privacy and data protection laws), or the laws and regulations of each participating country, whichever affords greater protection for the study subjects
- 21 CFR Part 11 (Electronic Records, Electronic Signatures)
- 21 CFR Part 54 (Financial Disclosure by Clinical Investigators)
- The procedures described with in this CIP
- Local Ethics Board requirements

All participating geographies will make study data available to the regulatory body such as FDA or competent authority if the regulatory body deems an onsite inspection necessary. The regulatory body will be able to inspect records at clinical centers around the world to resolve any uncertainties about whether the study was conducted in accordance with good clinical practice.

In addition to the regulatory requirements outlined above, the study will be conducted in compliance with relevant local laws. These include but are not limited to:

Medtronic Confidential

- In the United States, US FDA 21 CFR Parts
 - 50: Protection of Human subjects, 56: Institutional Review Boards and 812: Investigational Device Exemptions
- In Europe, Declaration of Helsinki 2013, the Competent Authority requirements, the Medical Device Directive (MDD) 93/42/EEC and ISO 14155:2011 with the exception stated earlier in this Section
- In Canada, the Medical Devices Regulations, Mandatory Medical Device Problem Reporting 59(1), 59(2), 60(1)
- In Japan, the study will be conducted in compliance with MHLW Ordinance No. 36, 2005 and related laws and regulations

The study will be publicly registered prior to first enrollment in accordance with the 2007 Food and Drug Administration Amendments Act (FDAAA) and Declaration of Helsinki on <http://clinicaltrials.gov> (PL 110-85, Section 810(a)).

Approval of the Clinical Investigation Plan (CIP) is required from the following groups prior to any study procedures at a study center:

- US Food and Drug Administration (FDA) or regulatory authority
- Pharmaceuticals and Medical Device Agency (PMDA) (if applicable)
- Medtronic
- Principal Investigators (where required by local law)
- An independent IRB/MEC

Similarly, approval of subsequent revisions to the CIP is required at each study center from the above mentioned groups prior to implementation of the revised CIP at that center.

19. Study Administration

19.1. Monitoring

It is the responsibility of Medtronic to ensure proper monitoring of this clinical study. Trained Medtronic personnel or delegates appointed by Medtronic may perform study monitoring at the study center in order to ensure that the study is conducted in accordance with the CIP, the Clinical Trial Agreement, and applicable regulatory and local requirements. Medtronic, or delegates, must therefore be allowed access to the subjects' case histories (clinic and hospital records, and other source data/documentation) upon request as per the PIC Form, Research Authorization (where applicable) and Clinical Trial Agreement. The Principal Investigator should also be available during monitoring visits.

Frequency of monitoring visits may be based upon subject enrollment, duration of the study, study compliance, number of adverse events, number of deviations, findings from previous monitoring visits and any suspected inconsistency in data that requires investigation. Regulatory documents may be reviewed at each study center. Monitoring for the study may include, but not limited to, site qualification visits, site

Medtronic Confidential

initiation visits, interim monitoring visits, and closeout visits, will be done in accordance to the study-specific monitoring plan.

Monitoring visits may be conducted periodically to assess center study progress, the Investigator's adherence to the CIP, regulatory compliance including but not limited to IRB/MEC approval and review of the study, maintenance of records and reports, and review of source documents against subject CRFs. Monitors review center regulatory and study compliance by identifying findings of non-compliance and communicating those findings along with recommendations for preventative/corrective actions to center personnel. Monitors may work with study personnel to determine appropriate corrective action recommendations and to identify trends within the study or at a particular center.

19.2. Data Management

Data will be collected using an electronic data management system for clinical studies. eCRF data will be stored in a secure, password-protected database which will be backed up nightly. Data will be reviewed using programmed and manual data checks. Data queries will be made available to centers for resolution.

Data collected by Holters, TTMs and 12-lead ECGs will be managed and over-read by a core lab. Final classification of recurrent AF/AT/AFL will be stored in the study database.

Study management reports may be generated to assess data quality and study progress. At the end of the study, the data will be frozen and will be retained indefinitely by Medtronic.

All records and other information about subjects participating in the study will be treated as confidential. Data will be transferred and processed by Medtronic or a third party designated by Medtronic in a key coded form, unless it's impossible to make it anonymous, for instance, where the subject's name cannot be removed from the data carrier, such as fluoroscopy images. In the case that de-identifying is impossible or involves a disproportionate effort, files containing personal data of subjects shall only be made accessible to authorized persons (secured role-based access).

Procedures in the CIP require source documentation. Source documentation will be maintained at the center. Source documents, which may include worksheets, subject medical records, console files, must be created and maintained by the investigational center team.

The data reported on the eCRFs shall be derived from source documents and be consistent with these source documents, and any discrepancies shall be explained in writing. The eCRF may be considered source for the following data collection elements:

Medtronic Confidential

- Time of isolation of the cryoablation catheter
- Esophageal temperature
- Investigator assessment of adverse event or death relatedness and severity
- Date center became aware of the adverse event, device deficiency or death
- Reason for study deviation
- Database generate patient reference ID

When copies or print-outs of the source documents are made, center personnel must sign and date any copies or printouts of original source documents with a statement that this is complete and true reproduction of the original source document.

The sponsor or a regulatory authority may audit or inspect the study center to evaluate the conduct of the study. The clinical Investigator(s)/institution(s) shall allow study related monitoring, audits, IRB/MEC review and regulatory inspection by providing direct access to source data/documents.

